Primary Aim: To determine if a 48 hour maximum dwell time reduces bacterial contamination and biofilm formation of feeding tubes, feeding tube hubs, and intraluminal fluid in premature VLBW infants. **Primary hypothesis**: Feeding tubes which remain in place 0-48 hours will have less contamination and less biofilm formation compared to those left in place for 7 days.

Aim 2: Compare gastrointestinal microbial dysbiosis and inflammation between Group 1 and Group 2. **Hypothesis:** Infants in Group 1 will have less GI microbial dysbiosis and inflammation compared to Group 2.

Aim 3: Determine the effect of feeding tube dwell time and feeding tube contamination, and biofilm formation on selected health outcomes in premature VLBW infants. **Hypothesis:** Infants in Group 1 will have lower odds for necrotizing enterocolitis and late onset sepsis, and improved nutritional outcomes compared to Group 2.

5. Research Plan:

A randomized controlled trial will be conducted to determine whether feeding tube dwell time is associated with level of feeding tube contamination. Infants will be randomly assigned to have their feeding tubes removed at 0-48 hours or 7 days for the first 4 weeks of life. The feeding tube lumen, interluminal liquid and hub will be analyzed for level of contamination.

Sample and Setting

The proposed study will follow a prospective cohort (N =151) premature VLBW male and female infants for 4 weeks following birth. If the mother is providing breast milk to her infant, she will also be included in the study since she will be providing 2 samples of her breast milk for analysis.

Inclusion criteria are: 1) be born to a mother who is at least 18 years of age and English or Spanish speaking, 2) born at \leq 30 weeks 3) have a birthweight \leq 1500 grams, 4) be born to a mother who is COVID Negative, 5) have a feeding tube placed within 24 hours of birth and 5) be expected to require a feeding tube for 4 weeks following birth.

Exclusion criteria are: 1) Infant with known congenital GI anomalies, (2) are not expected to live, or (3) Infants will be withdrawn from the study if they require abdominal surgery for GI morbidities.

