DNA Extraction and 16S rRNA sequencing. DNA will be extracted from cells pellets obtained after tube processing. DNA will be extracted using PowerFecal DNA isolation kit (MO BIO Laboratories). DNA will be quantified using a Nanodrop spectrophotometer (Thermo Scientific, Wilmington, DE). V4 universal primers will be used for 16S rRNA amplification and subsequent Illumina MiSeq sequencing. Samples will be amplified in 25 µl reactions containing 0.5 Units Phusion High-Fidelity Polymerase (New England Biolabs, Ipswich, MA), 1X Phusion HF Reaction Buffer, 0.75 µl DMSO, and 0.2 mM each dNTP. Triplicate PCR amplifications will be pooled for each sample, and cleaned with a QIAquick PCR Purification kit (Qiagen). Two hundred nanograms of each cleaned amplicon library will be submitted for sequencing at the ICBR core facility at the University of Florida. Sequencing will be performed on an Illumina MiSeq with a 300-bp paired-end protocol, using single indexing.

Microbiome 16S rRNA Gene Analysis. Sequencing reads will be parsed by Illumina index at the sequencing center. Paired reads will be merged, and primers and adaptors will be removed using a combination of tools in cutadapt, Galaxy, and eautils. Parsed raw sequencing reads will be made available to the scientific community after publication through NCBI's Sequence Read Archive (SRA). Sample names will be added to the definition lines of sequencing reads using sed and concatenated into one fasta file, to make them compatible for analysis in QIIME v1.9. Clustering of Operational Taxonomic Units (OTUs) at 97% similarity will be performed with the subsampled open-reference OTU picking method, with no removal of singletons. The Greengenes reference dataset version 13.8 will be used as the reference for OTU picking and for taxonomy assignment with uclust. Community structure will be analyzed in R with phyloseq and will be plotted with ggplot2. Analysis of similarities (ANOSIM) will be performed in R using VEGAN v2.0-8. Statistical significance of QIIME profiles will be assessed using STAMP.

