Gastric/Stool/Sputum/Sampling. Gastric sample of at least 1.0-2.0 mL will be collected weekly by the research coordinator, immediately following insertion of a new feeding tube, by gently aspirating gastric contents from the feeding tube into a syringe. Gastric aspiration assessment for feeding tube placement as per NICU protocol. One baseline pH will be obtained at start of study. To assess gastric pH, the research coordinator will use one-two drops of the gastric sample to test using Hydrion pH strips and Fischer Scientific Horiba LAQUA twin pH 11 meter. The rest of the gastric sample will be used to analyze the microbiome and level of inflammatory markers. Stool samples will be collected weekly by the research nurse and pH check of sample will be done. Following collection, all samples will be placed in a sterile specimen container and immediately frozen at -80 degrees Celsius for later analysis. This team has extensive experience in the collection of gastric aspirates, and stool from premature VLBW infants in the NICU as well as the analysis of inflammatory markers and 16S rRNA sequencing of these samples. Oropharyngeal swabs will be collected weekly by the research coordinator (a registered nurse experienced in the care of critically ill infants) by placing a tiny soft brush into the infant's mouth and gently rotating the swab to collect the infant's saliva.

Microbiota Sequencing and Analyses: DNA from samples will be extracted and analyzed as described above (see Aim 1).

Inflammatory Response. The samples will be analyzed for inflammatory markers using a combination of multiplex technologies using the BioRad Bio-Plex platform as well as S100A12 and calprotectin immunoassays.

Statistical Analysis

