Data integrity will be evaluated using descriptive statistics (e.g.: means, standard deviations, frequencies, percents, range) appropriate for measurement level. Checks for implausible or outof-range values, distributional forms, the presence and distribution of censored values (e.g.: inflammatory markers), and missingness will be performed. Data transformations (e.g.: Box-Cox family of transforms) will be made, if required, based on evaluation of model fit and tenability of assumptions. If applicable, regression techniques which can accommodate censored variables (e.g. MPLUS version 8 or higher)⁵⁸ will be employed. Selected variables (e.g.: type of feed (mother's breast milk or donor breast milk), whether NPO, antibiotic use, gestational age, chronological age, gastric pH and sex) will be screened for potential inclusion as covariates in each of the statistical models tested. Associations between each potential covariate and the respective dependent variable will be examined, and only those variables having a p<.10 association and whose inclusion improves model fit will be retained. The general modeling strategy will be a generalized linear mixed model (GLMM) approach. A GLMM is able to accommodate different numbers of measurements between subjects, utilize data from subjects when some of the data is missing (that is, subjects with some missing data points will not be dropped from analysis), can incorporate time-varying covariates, flexible covariance structures, and a variety of dependent variable distributions (including dichotomous), and thus will be able to accommodate the analyses proposed. Model fit and strength of association will be evaluated using Vonesh's GOF macro for SAS. Our primary goal will be to assess differences in marginal least squares means between the dwell time groups. All analyses will be performed using SAS software version 9.4 or later. Statistically significant interaction effects will be evaluated using simple main effects analyses via the SLICE option available in the SAS/STAT GLMM procedures. Due to the number of inferential tests planned, it is not practical to maintain a 5% experiment-wise Type I error rate; however, significance levels will be adjusted to maintain a model-wise 5% Type I error rate through use of a Benjamini-Hochberg approach.

Data Entry and Management

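### The 16S tests (ANOSIM, STAMP) have no stated sample unit; pooling weekly samples as independent to compare dwell groups would inflate type I error, so make the infant the unit

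*Combined protocol and SAP*

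**What the plan says.** - **Microbiome 16S rRNA Gene Analysis** names the tests: "Analysis of similarities (ANOSIM) will be performed in R using VEGAN v2.0-8. Statistical significance of QIIME profiles will be assessed using STAMP". It gives no grouping factor, sample unit or permutation restriction, and does not say which test within STAMP is meant.
- **Microbiota Sequencing and Analyses** carries this pipeline to the infant samples: "DNA from samples will be extracted and analyzed as described above (see Aim 1". Those samples are repeated. For example, Gastric/Stool/Sputum/Sampling states: "Stool samples will be collected weekly by the research nurse and pH check of sample will be done". The variables table under Data Entry and Management also has gastric and stool sequencing every week for four weeks.
- **Research Plan** makes the infant the randomised unit: "Infants will be randomly assigned to have their feeding tubes removed at 0-48 hours or 7 days for the first 4 weeks of life". The Aim 2 hypothesis is a contrast between arms: "Infants in Group 1 will have less GI microbial dysbiosis and inflammation compared to Group 2".
- **Statistical Analysis** makes a GLMM the general strategy and adds: "Our primary goal will be to assess differences in marginal least squares means between the dwell time groups". On multiplicity, "significance levels will be adjusted to maintain a model-wise 5% Type I error rate through use of a Benjamini-Hochberg approach". On software, "All analyses will be performed using SAS software version 9.4 or later". It does not mention ANOSIM or STAMP, and it names no scalar dysbiosis outcome for the GLMM.

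**The concern.** Dwell group is constant within an infant, so information about it comes from the number of infants and not from the number of specimens. ANOSIM with freely permuted labels, or a two-sample test on every specimen, counts four samples from one infant as four independent observations. Stable differences between infants, which exist whatever the dwell time, then count as evidence about dwell time. A chance imbalance between arms could be reported as a dysbiosis effect under Aim 2.

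The Statistical Analysis section has a suitable repeated-measures model but does not link it to these tests. Its statement that everything runs in SAS, against R and STAMP in the 16S section, leaves unclear whether its handling of repeated measures reaches them. A GLMM can test a diversity index or a taxon, but it cannot test a dissimilarity matrix. ANOSIM therefore needs its own rule on the unit.

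**Working it through.** **The plan's own figures.** The documents give no power or error rate for the 16S tests. The stated power (lower limit .97) is for the culture endpoint and cannot be reproduced, because the pilot means and covariance matrix are not given. Its count of data points does reproduce: 4 weeks × 5 sections × 5 colony types = 100.

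**Inputs.** From the documents: m = 4 weekly samples per infant per site; randomisation by infant; 134 enrolled with 10% loss, so 134 × 0.9 = 120.6, taken as 120. Assumed: 1:1 allocation (60 per arm), the within-infant correlation ρ, and the community models. Sample and Setting gives N = 151, not 134; the formula in step 1 does not depend on N.

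**Step 1: per-taxon test on all samples.** The variance of an arm mean is larger than the test assumes by DEFF = 1 + (m − 1)ρ = 1 + 3ρ. The actual level of a nominal two-sided 5% test is 2[1 − Φ(1.96/√DEFF)].

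| ρ | DEFF | 1.96/√DEFF | Actual level |
|---|---|---|---|
| 0 | 1.0 | 1.96 | 5.0% |
| .1 | 1.3 | 1.72 | 8.6% |
| .2 | 1.6 | 1.55 | 12.1% |
| .5 | 2.5 | 1.24 | 21.5% |

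Simulated Welch tests on log relative abundance agree (8.4-8.5%, 11.9-12.2% and 21.4-21.5% for ρ = .1, .2, .5). On raw relative abundance they are somewhat lower (6.3-7.3%, 8.4-10.4%, 16.0-18.9%).

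**Step 2: ANOSIM under a true null.** Bray-Curtis distances, 30 log-normal taxa, 199 permutations, 1,000 trials per cell. The even community has equal log means and SD 1; the dominated community has log means from +3 to −3 and SD 1.5. Rejection rates (%):

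| Method | Community | ρ = 0 | .1 | .2 | .5 |
|---|---|---|---|---|---|
| All samples, free permutation | even | 5.5 | 21.7 | 48.1 | 84.6 |
| All samples, free permutation | dominated | 3.7 | 12.1 | 23.9 | 60.7 |
| Labels permuted by whole infant | even | 5.7 | 4.8 | 5.1 | 5.2 |
| Labels permuted by whole infant | dominated | 3.3 | 3.6 | 4.0 | 5.3 |
| Weekly, Benjamini-Hochberg over 4 weeks | even | 4.2 | 4.4 | 2.7 | 4.8 |
| Weekly, Benjamini-Hochberg over 4 weeks | dominated | 4.0 | 4.5 | 5.7 | 4.5 |

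Per-taxon t-tests on infant means, which equal the balanced random-intercept model, reject 4.9-5.1% throughout. A different model (134 infants, 20 normal features, Euclidean distance, 200 trials) points the same way: pooled ANOSIM rejects 4.5% at ρ = 0, about 27% at .1, 69% at .3 and 89% at .5, against 2.5-6.0% with whole-infant permutation.

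**Step 3: unequal sample counts** (ρ = .2, 400 trials, even/dominated). With 15% of samples missing in both arms, whole-infant permutation rejects 4.0%/3.3%. With 10% missing in Group 1 and 30% in Group 2, it rejects 14.7%/9.2%, because the number of samples then carries information about the arm. The weekly form with Benjamini-Hochberg stays at 4.8%/4.0%.

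**Step 4: power of the two infant-level forms** (6 of 30 taxa shifted by 0.5 SD, ρ from .1 to .5). In the even community the weekly form detects the shift in 99% of trials at ρ = .1 and .5. In the dominated community, with mid-abundance taxa shifted, it detects 26-28% against 50-89% for whole-infant permutation. A second run of that setting (150 trials per cell) gave 22-27% against 51-92%.

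**The case against.** The strongest reply is that no error is stated. The 16S section describes a laboratory and bioinformatics pipeline. It does not say that weekly samples are pooled or that dwell group is the ANOSIM factor; other factors, such as tube portion or milk source, are possible. The Statistical Analysis section already makes a GLMM with dwell-group least squares means the general strategy, adds Benjamini-Hochberg control, and says the GLMM can accommodate the proposed analyses. On that reading the arm comparison under Aim 2 is already a repeated-measures model, and the SAS statement against R and STAMP is only a wording inconsistency.

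Much of this stands. A reader might infer that the plan analyses specimens as independent, that it has no method for repeated measures, or that the software mismatch shows clustering will be ignored. The documents support none of these. What remains is that the only tests named for 16S data have no stated unit, the GLMM is not linked to them, and no dysbiosis outcome is named for it. An analyst could pool the samples without departing from the text.

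The sizes also rest on assumed correlations, held constant over four weeks. The 85% figure needs the highest correlation and evenly abundant taxa, and the STAMP figures assume a Welch-type test that the plan does not name.

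**Conclusion.** The point holds in conditional form. If ANOSIM or sample-level STAMP tests compare dwell groups on all weekly samples as independent, type I error is inflated at any positive within-infant correlation. For assumed correlations of .1 to .5 the level is about 9-22% per taxon (closed form) and about 12-85% for ANOSIM, depending on the community model. At zero correlation there is no inflation. The direction is firm; the size is illustrative, because the documents give no correlation.

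The reach is Aim 2 and the other 16S comparisons by arm. A reader might extend it to the primary result, but the culture GLMM and its power statement do not use these tests and are unaffected.

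One neighbouring matter is separate: Sample Size Determination/Power Analysis describes weekly tube measurement, while the variables table has analysis after each tube removal. That sampling inconsistency needs reconciling whether or not samples are correlated.

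This is a cheap improvement that the plan should adopt, not a fatal fault.

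**What to change.** For comparisons between dwell groups:

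1. Test taxa and diversity indices with the GLMM of the Statistical Analysis section, with an infant random effect, in place of sample-level STAMP tests. State that this GLMM, on a dysbiosis index named in advance, carries the Aim 2 inference.
2. Keep ANOSIM as supportive, with the infant as the unit. Where infants contribute equal numbers of samples, permute group labels by whole infant. Otherwise run it by study week with one sample per infant, and apply Benjamini-Hochberg across the weeks.
3. Note in the Statistical Analysis section that ANOSIM is run in R as an exception to SAS.

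Separately, reconcile the weekly tube measurement with the analysis of each removed tube.

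**Cost.** A few sentences and some analysis code; no new data. P-values become larger. The weekly form can lose substantial power when the shifted taxa are not dominant (about 26-28% against 50-89% in the assumed example), which is why whole-infant permutation comes first where sample counts are equal.

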Sample Size Determination/Power Analysis: The primary aim of this study is to test for associations between feeding tube dwell time and the bacterial load present in the feeding tube. Pilot study results were used to estimate variance for the log transformed values of bacterial load observed in cultures. The study employs a repeated measures design, with measurements performed on each neonate each week of the 4 week study duration. For the primary bacterial contamination aim, each measurement consists of measures from 5 individual feeding tube sections for 5 individual colony types, providing a total of 100 within-subjects data points per neonate. Given the repeated measures design and the incorporation of selected covariates, a Generalized Linear Mixed Model (GLMM) analysis is planned for the primary aim. The data derived from the pilot study of 31 feeding tubes informed the covariance structure and means vectors for entry into PASS 14's procedure which estimates mixed models power using simulation. Using a .005 level of significance (in recognition of the multiple inferential tests), 400 simulation samples, a minimum detectable difference of 3.0 (natural log transformed colony forming units), and employing the pilot data to inform mean vectors and the unstructured covariance matrix for the simulations, the lower 99% confidence limit for power is .97 for the Dwell Group by Colony Type interaction, which is of primary interest. To accommodate the anticipated 10% loss due to surgery or death, 134 neonates will be enrolled. If mothers are providing breast milk samples, 151 mothers would also be enrolled.

Standard Infant Feeding Protocol

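### ANOSIM has no companion dispersion test, so a significant result cannot be attributed to a shift in the average microbial community

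*Combined protocol and SAP*

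**What the plan says.** The section on 16S rRNA gene analysis gives the community-level test one sentence: "Analysis of similarities (ANOSIM) will be performed in R using VEGAN v2.0-8". The next sentence adds a profile-level analysis: "Statistical significance of QIIME profiles will be assessed using STAMP". Neither names a dissimilarity measure, a grouping factor, a permutation scheme or a rule for interpreting a significant R.

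The later section on microbiota sequencing sends the gastric, stool and oropharyngeal samples down the same route: "DNA from samples will be extracted and analyzed as described above (see Aim 1". Those samples serve Aim 2, whose hypothesis is directional: "Infants in Group 1 will have less GI microbial dysbiosis and inflammation compared to Group 2". Dysbiosis is not defined, either as a shift in composition or as a change in variability.

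The Statistical Analysis section covers the mixed models, where the target is a difference in means between dwell groups, and multiplicity: "significance levels will be adjusted to maintain a model-wise 5% Type I error rate through use of a Benjamini-Hochberg approach". No section names a test of multivariate dispersion.

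**The concern.** ANOSIM permutes group labels over ranked dissimilarities. The null it generates is that samples from the two groups are exchangeable in every respect, in spread as well as in average composition. A rejection therefore says that the two distributions differ, but not how.

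Aim 2 asks whether one group's community is less dysbiotic. Most readers will take a significant community test as evidence that the typical community moved. If one group's infants are merely more heterogeneous around the same centre, that conclusion would be wrong, and nothing in the plan would reveal it. Under unequal group sizes the reverse can happen too: ANOSIM can miss a real shift. The 16S comparisons of tube, gastric, stool and oropharyngeal samples are all affected.

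**Working it through.** **Plan's own figure.** None is given for ANOSIM, so there is nothing to reproduce.

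**Inputs.**
- Groups: "Infants will be randomly assigned to have their feeding tubes removed at 0-48 hours or 7 days". The allocation ratio is not stated; 1:1 is assumed unless noted.
- Size: "To accommodate the anticipated 10% loss due to surgery or death, 134 neonates will be enrolled". 120 / 0.90 = 133.3, which rounds up to 134, so about 120 infants are analysed, or 60 per group. The Sample and Setting section gives 151 instead; the Gaussian check below is repeated at 67 per group (134 analysed).
- Level: 0.05 for a single test.
- Assumed: one sample per infant, the distances, and the ratio of between-infant SDs (1.0 to 1.5 in the main table).

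**Statistic.** R = (mean between-group rank − mean within-group rank) / (M/2), with M = n(n−1)/2. For n = 120, M = 120 × 119 / 2 = 7,140 and M/2 = 3,570. With 60 per group there are 2 × (60 × 59 / 2) = 3,540 within-group pairs and 3,600 between-group pairs.

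**Why spread matters.** Take 10 Gaussian dimensions, equal centroids, and SDs 1 and 1.2. Expected squared distances are 2 × 10 × 1 = 20 and 2 × 10 × 1.44 = 28.8 within the groups, and 10 × (1 + 1.44) = 24.4 between them. That is exactly midway, so a balanced test on squared Euclidean distances is neutral. Ranking does not preserve the midpoint: mean simulated R was 0.0195, against −0.0001 at equal spread.

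**Main simulation.** 60 per group, 20 taxa, equal mean log-ratios, 199 permutations, mostly 200 to 300 trials per setting. Entries are rejection rates; ranges span repeated runs.

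| SD ratio | 1.0 | 1.1 | 1.2 | 1.5 |
|---|---|---|---|---|
| Aitchison, ANOSIM | 2-8% | 15-19% | 72-76% | 100% |
| Aitchison, PERMANOVA | 2-7% | 2-4% | 5% | 4-6% |
| Bray-Curtis, ANOSIM | 5-8% | 8-9% | 16-19% | 86-87% |
| Bray-Curtis, PERMANOVA | 5-7% | 7-8% | 12% | 76-82% |

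With 300 trials the Monte Carlo standard error is √(0.75 × 0.25 / 300) = 2.5 points at 75%, and √(0.17 × 0.83 / 300) = 2.2 points at 17%.

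**Other models, ANOSIM.**
- Gaussian, SD ratio 1.0 / 1.1 / 1.2 / 1.3 / 1.5: 0.05 / 0.13 / 0.48 / 0.92 / 1.00 at 60 per group, and 0.06 / 0.15 / 0.59 / 0.95 / 1.00 at 67.
- Dirichlet-multinomial, identical mean proportions, Bray-Curtis, 60 per group, precision 5 v 5 / 5 v 4 / 6 v 4 / 5 v 2.5 / 10 v 2.5: 0.05 / 0.07 / 0.26 / 0.67 / 1.00.

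**Imbalance.** With 45 and 75 infants there are 45 × 44 / 2 = 990 and 75 × 74 / 2 = 2,775 within-group pairs, so the larger group supplies 2,775 / 3,765 = 74% of them. If it is the more variable group, the mean within-group rank rises and R turns negative. In the Gaussian model at ratio 1.2, mean R was −0.0848 with no rejections; with the smaller group more variable it was 0.129, with 99% rejected. On Aitchison distance at ratio 1.2, a split of 63 and 57 gave 99% with the smaller group more variable and 1-2% with the larger. With a real shift, 45 v 75 and the larger group more variable, ANOSIM detected 0% and PERMANOVA 87%.

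**Does PERMANOVA alone cure it?** The main table uses exact proportions. The plan will have read counts, with singletons kept. With multinomial reads, a 0.5 pseudocount, equal mean log-ratios and 60 per group, PERMANOVA on Aitchison distance rejected:
- 20 taxa, 1,000 reads: 8-12% at ratio 1.2, 38-39% at 1.5.
- 100 taxa, 5,000 reads: 19-23% and 100%.
- 100 taxa, equal spread, depth 5,000 v 2,500: 45-51%; depth 5,000 v 1,000: 100%. ANOSIM on Bray-Curtis gave 9% and 7% for these two depth contrasts.

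**Does a dispersion test help?** In the Gaussian runs at 60 per group, a distance-to-centroid test rejected 0.04 / 0.63 / 0.99 / 1.00 / 1.00 at ratios 1.0 / 1.1 / 1.2 / 1.3 / 1.5, so it identifies spread as the cause where ANOSIM is most misleading.

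**The case against.** A reader might infer that ANOSIM is invalid or has an inflated Type I error rate. The documents and the simulations do not support that. For its own null of no difference of any kind it holds its level (4.3% in 1,000 trials at equal spread). Under randomisation a difference in spread is itself an effect of dwell time. The fault lies in what may be concluded from a rejection.

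A reader might also infer that the trial will report a false shift. The plan does not say that dwell group is the ANOSIM factor, that a significant R will be read as a shift, or that dysbiosis means a shift. Nor do the documents show that the arms will differ in spread; the idea that low-load communities vary more has no support there.

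A third tempting step is to replace ANOSIM with PERMANOVA and stop. On Bray-Curtis the two behave almost alike, and on Aitchison distance with sparse counts PERMANOVA also rejects for unequal spread or depth. That part of the objection stands and shapes the fix.

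Two further limits stand. Equal mean log-ratios with unequal SDs do not give equal mean proportions, so some Bray-Curtis rejection in the main table reflects a real difference in mean proportions, although the Dirichlet model, which holds those means equal, still shows the effect. And rejection is not universal: ANOSIM becomes conservative when the larger group is the more variable. STAMP also examines the profiles, but the plan does not present it as a check on dispersion.

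**Conclusion.** The point holds as one of interpretation. As written, if dwell group is the factor, a significant ANOSIM cannot be attributed to a shift in the average community, and a non-significant one in unequal groups cannot rule a shift out. At an SD ratio of 1.2 with 60 per group, the chance of rejecting with equal mean log-ratios is about 75% on Aitchison distance and about 17% on Bray-Curtis. At a ratio of 1.1 it is 15-19% and 8-9%. The 99% and 1-2% figures for slight imbalance apply to Aitchison distance at ratio 1.2.

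All of these rest on assumed SD ratios, assumed distances, one sample per infant and, except where imbalance is stated, 1:1 allocation; the documents supply none of them. Using 134 analysed infants instead of 120 does not change the conclusion. The culture-based primary mixed model and its power are untouched. The change is worth making before the sequence data are analysed.

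**What to change.** In the 16S analysis section, and by reference for the Aim 2 samples:

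1. State the distance and that dwell group is the factor.
2. Use PERMANOVA as the between-group test, with labels permuted by infant, since the infant is the randomised unit and contributes repeated samples.
3. Always pair it with a test of multivariate dispersion on the same distances.
4. Fix the reading in advance. Claim a composition shift only when PERMANOVA is significant and the dispersion test shows no material difference in spread. If spread differs, report a difference in community distribution and give the dispersion difference as its own result, without calling it a shift.
5. Do not rely on PERMANOVA alone with any distance. Compare read depth by arm, equalise it if it differs (for example by rarefying), and repeat the result on a second distance such as Bray-Curtis.

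The cost is SAP wording and a little more analysis of data already planned. With a true shift and equal spread, on Aitchison distance with exact proportions, power is about the same (97.5% for ANOSIM and 98.5% for PERMANOVA; 96% for both in a repeat). At an SD ratio of 1.5 PERMANOVA has 84% against ANOSIM's 100%, but ANOSIM also rejects 100% there with no shift. The real price is that fewer results can be called a shift.
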